## **18) Consent Process**

Informed consent will be obtained at the bedside of the patient on the COVID-19 acute care, telemetry-monitored covid positive unit who is assigned to the intervention by a member of the research team. This process will be as follows:

- An order to self-prone and verify consent for proning will be entered into the computer by the doctor.
- The research team member will bring a paper copy of the consent to the patient (copy stored on the unit, attached to this submission), and fully explain the consent.
- The patient will be given the opportunity to ask questions and ask for further clarification.
- At the end of the consent process, the patient will be asked to explain the intervention back to the member getting consent.

This process should take in total about 15 minutes, and will be the same for every patient assigned for the intervention group. The patient will be allowed to decline the intervention.

If the patient cannot speak, read, or write English, an alternative consent will be provided in their language of choice, and consent will be obtained through the facility's interpretation device.

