##### **Exclusion Criteria:**

The exclusion criteria included those that are not COVID 19 positive. Those patients that are COVID -19 positive and in an ICU setting, or in need of ICU level respiratory treatments and interventions would be excluded, as well as those with respiratory distress (defined as immediate need for intubation, respiratory rate over 35, PaCO2 level above 65, and accessory muscle use) or in hemodynamic instability (systolic blood pressure below 90) or arrhythmia. The researchers would also exclude patients that have agitation or who have altered mental status, unstable spine/thoracic injury or recent abdominal surgery, significant pressure ulcers (above stage 1), pregnant patients past the 2nd trimester, and patients that have concerning neurological issues (such as seizures). Patients that are unable to change positions independently will also be excluded.

*Describe how individuals will be screened for eligibility.*

This is a single-center prospective study which will be conducted over a period of 8 months on a telemetry-monitored, acute care unit in a large tertiary teaching hospital in Houston, Texas. Randomized sampling will be used to recruit and consent 96 patients that meet the study inclusion criteria (48 in the intervention group and 48 in the control group). This study will seek approval from the Common Spirit Health Institutional Review Board, and all participants receiving the intervention will be consented (see consent form attached).

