2. If the patient tolerates the proning well, the procedure can continue and the RN will set the timer for 2 hours, enter the patient's oxygen saturation into the EMR, and document the position (prone or supine) on the checklist. O2 saturation will be documented at least every 4 hours per unit protocol.
3. The 2 hour timer will be reset each set of 2 hours by the nursing staff, and the intervention will continue until the end of the study period or until the patient is discharged or transferred from that unit.
4. The checklists will be placed in a binder at the nurses' station at the end of each shift and collected daily by a member of the research team.
5. This intervention for each "proned" patient will continue until either of the following occur: either the patient is discharged or transferred to a lower level of care from the acute care floor, or 14 days have passed.
6. A retrospective chart review will be completed by the research team to ascertain length of stay on the acute care, telemetry monitored unit, as well as the need for escalation of respiratory care. Escalation is defined by a need for oxygen requirements above 6 liters of oxygen on the nasal cannula.

*If the patient is assigned to the control group, that patient will receive the standard of care treatment designated by BSLMC policy per their condition on the COVID-19, acute care, telemetry-monitored unit.*

**Data Analysis:** Retrospective data analysis will be conducted by the research team with data collected from the electronic medical record as well as the checklists (oxygen saturation, demographics, proning protocol) for both the interventional and control group. See attached documents for consent/proning protocol documents.

This study will be a prospective cohort study in which data will be collected on subjects for the designated time period. Data will be collected from the electronic medical record as well as the checklists. Data collection will include basic patient demographics, specifically age and gender, height, weight and ethnicity. Clinical data to be collected include O2 saturation, respiratory support methods, proning duration/compliance, presence of hospital acquired pressure injuries,

and need to escalate care to ICU, including initiation of mechanical ventilation. The same data will be collected for the control group - except for proning duration/compliance as they will not receive this intervention.

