## **9) Data and Specimen Banking**

The data obtained from this study will be basic patient demographics, specifically age and gender, height, weight and ethnicity. The patient medical record number, name, and date of admission/discharge are included as PHI necessary to complete this study. Clinical data to be collected include O2 saturation, respiratory support methods, proning duration/compliance, presence of hospital acquired pressure injuries, and need to escalate care to ICU, including initiation of mechanical ventilation. The REDCap project IDs are 2817 and 3682 for reference.

Upon consent to the study, the patient's medical record number will be recorded as the principal identifier, and the above demographic data will be collected from the electronic medical record. This information will be coded to a personal ID generated by the researchers' REDCap software by the principal investigator or members of the research team. The clinical data obtained during and after the intervention will be recorded from the electronic medical record and also linked to the personal ID in the REDCap software.

The list linking the medical record number to the personal ID will only be handled by members of the research team and will be destroyed electronically upon completion of data collection - approximately 8 months after the initial start of the study. This is to allow for easy access of associated data as the researchers update the ID profiles. All of the members of the research team have completed CITI training, as well as financial conflict of interest records.

The researchers do not anticipate any incidental findings that would impact the outcome of this study or the care of the patient. If the patient started the study and then wished to have their data removed, the patient would communicate that to the nurse assigned, who would then call the principal investigator (number provided to the unit). The investigator would then delete the profile from REDCap and remove the medical record number from the study records.

Data collection will proceed as follows:

1. Every calendar day after the patient has been consented and the intervention is occurring, the nurse assigned to the patient will chart O2 saturation, any presence of hospital acquired pressure injuries, and need to escalate care. This data will be recorded in the electronic medical record, and members of the research team will daily update the REDCap profile with that data.

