### ***Waiver or Alteration of the Consent Process***

For our patients assigned to the control group, a waiver of consent will be requested.

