## **19) Process to Document Consent in Writing**

The study should present no more than minimal risk of harm to subjects. Nevertheless, the researchers will be collecting a written informed consent from the study participant, and storing those in a secure filing cabinet until the study analysis is complete (approximately 1 year). The consent document is attached to this submission.

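### Consent is sought after assignment and in the prone arm only, and the protocol does not say that an assigned patient who declines is kept, so the primary comparison may not be between the randomized groups

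*Protocol*

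**What the plan says.** **Assignment comes first.** Section 8 (Procedures Involved) randomizes patients on admission to the unit. Section 15 (Resources Available) has the team member obtain consent once random assignment has identified an intervention patient, and Section 14 (Setting) describes consenting patients who are already randomly assigned.

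**Consent applies to one arm.** Section 18 (Consent Process) covers the patient assigned to the intervention and adds: "The patient will be allowed to decline the intervention". For the other arm it says: "For our patients assigned to the control group, a waiver of consent will be requested". Section 8 collects the control data by retrospective chart review.

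**Prone-arm data start from consent.** In Section 9 (Data and Specimen Banking) the medical record number is recorded "Upon consent to the study", and the daily steps run "Every calendar day after the patient has been consented and the intervention is occurring".

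**Who is counted.** Section 4 says: "Randomized sampling will be used to recruit and consent 96 patients that meet the study inclusion criteria". That total includes the 48 controls, for whom Section 18 seeks a waiver.

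**Primary analysis.** Section 10 (Data Analysis Plan) calls the study a randomized controlled trial and compares time to discharge between the prone and not-prone arms by log-rank test, 48 per group.

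**The concern.** Randomization makes the arms comparable at the moment of assignment. Here a further choice, accepting or declining, comes after that moment and is offered in one arm only. If those who decline leave the prone arm while their counterparts stay among the controls, the arms differ by self-selection as well as by proning.

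Selection related to prognosis is plausible in either direction. Sicker patients may refuse because turning is hard, and fitter ones because they see no need. Section 12 (Risks to Subjects) itself lists discomfort, inconvenience and inability to hold the position.

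This goes beyond the choice of an analysis set. A later analysis plan can name the set, but it cannot use chart data for which no permission was obtained. That permission is settled by the protocol, the consent form and the waiver.

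**Working it through.** **1. The path of an assigned patient who declines**

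| Step | Assigned to proning, declines | Comparable patient assigned to control |
|---|---|---|
| Assigned on admission (Section 8) | yes | yes |
| Asked for consent (Section 18) | yes, after assignment | no, waiver requested |
| Described start of the record (Section 9) | at consent, which is not given | none described, but data are collected (Section 8) |
| Length of stay from chart (Section 8) | permission not stated | yes, if the waiver is granted |
| Rule on analysis | none visible | included |

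The nearest rule, Section 11 (Withdrawal of Subjects), concerns a patient who has started the study, and its process deletes the profile. It does not keep decliners.

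**2. The plan's own figure**

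Section 10 states 80% power with 48 per group for a 50% decline in time to discharge. With exponential times a halved time is a discharge hazard ratio (HR) of 2. Assuming two-sided 5%, the Schoenfeld count is 4 × (1.96 + 0.84)² / (ln 2)², which rounds up to 66 events; the Freedman count is 71. These are 66/96 = 69% and 71/96 = 74% of patients. The figure is plausible but cannot be uniquely reproduced, because alpha, sidedness and the control median are not stated. The point here does not depend on it.

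**3. Size if decliners are lost from the prone arm**

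The protocol gives no refusal rate and no prognosis of decliners, so every input below is an assumption. There is no proning effect; 48 accepters are compared with 48 unselected controls; the cap is day 14; the log-rank test rejects at |z| > 1.96. The discharge rate is ln 2/7 per day, multiplied by 0.4 in slow recoverers (40% of patients) and 1.3 in fast recoverers (60%). Overall refusal = 0.4 × slow refusal + 0.6 × fast refusal. Slow share among accepters = 0.4 × (1 − slow refusal) / (1 − overall refusal). For 60%/10% refusal this gives 0.24 + 0.06 = 30% overall and 0.16/0.70 = 23% slow, against 40% in controls.

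| Refusal slow/fast | Overall | HR, prone vs control | False benefit | False harm |
|---|---|---|---|---|
| 10/10% | 10% | 1.00 | 2.6% | 2.6% |
| 30/30% | 30% | 1.00 | 2.6% | 2.5% |
| 17.5/5% | 10% | 1.04 | 3.7% | 1.8% |
| 5/13.3% | 10% | 0.98 | 2.0% | 3.1% |
| 45/20% | 30% | 1.10 | 5.9% | 1.0% |
| 60/10% | 30% | 1.21 | 11.8% | 0.3% |
| 20/36.7% | 30% | 0.94 | 1.5% | 4.3% |
| 10/43.3% | 30% | 0.88 | 0.7% | 7.3% |

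HR above 1 means faster discharge in the prone arm. With a milder prognosis gap (multipliers 0.7 and 1.2), the 30% cases give HR 1.05 to 1.10 when slow recoverers refuse more, and 0.97 to 0.94 when fast ones do; two-sided error is 5.2% to 6.9%.

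A simpler model, in which decliners' discharge hazard is half that of accepters, gives two-sided error of 6.3% at 10% refusal and 13.5% at 30%. With equal prognosis it stays near 5%. When all assigned patients are kept, it is 4.7% to 5.5% in every case tried.

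**4. Counts**

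If the 96 are consenting patients, reaching 48 accepters means assigning 48/0.9 = 54 patients to proning at 10% refusal, or 48/0.7 = 69 at 30%.

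**The case against.** The strongest reply is that no passage excludes decliners. Three parts of it stand.

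- **Consent cannot be the only gate to a study record.** Controls are not asked for consent, yet Section 8 collects the same data on them apart from proning compliance. The consent-based steps in Section 9 may simply describe the workflow for treated patients. Length of stay comes from the chart ("A retrospective chart review will be completed by the research team to ascertain length of stay") and exists for every inpatient.
- **Declining the intervention need not mean declining the study.** Such a patient could remain, unproned, with zero compliance among the items collected ("respiratory support methods, proning duration/compliance"). Section 8 also speaks of consent to participation, which points the other way.
- **The consent form is not visible.** Section 19 says: "The consent document is attached to this submission". It, or the waiver, may already cover decliners' chart data.

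A reader might therefore infer too much in three ways: that the prone arm certainly holds accepters only, that the result is biased in favour of proning, or that a missing intention-to-treat definition is itself the fault. The documents support none of these. Loss of decliners is conditional, the direction is unknown, and an analysis set may properly be defined in a statistical analysis plan.

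What remains is that consent follows assignment in one arm only, and that the protocol text does not settle what happens to a decliner's data.

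**Conclusion.** The point holds conditionally. Consent after assignment, in the prone arm alone, is plain from the text. Loss of decliners is an inference. It follows unless declining means staying in the study unproned, or the consent form or waiver covers their chart data. If it does follow, the primary test compares accepters with all eligible controls and is not a comparison of the groups formed by randomization.

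The size is unknown. Under the assumed models there is no bias when refusal is unrelated to prognosis and little at 10% refusal. The upper figure of about 12% (13.5% in the simpler model) needs 30% refusal and a strong link with prognosis. This should be fixed before enrolment, but it does not invalidate the design.

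Separately, Section 4's statement that all 96 are consented conflicts with the control waiver in Section 18, and it leaves unclear whether the 96 are assigned or consenting patients.

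**What to change.** - State in Sections 9, 10 and 18 that every assigned patient who meets the eligibility criteria is analysed in the assigned arm whether or not proning is accepted, with length of stay taken from the chart. Record decliners as zero compliance and report their number.
- If it is not already covered, ask the IRB to include decliners' chart data in the waiver, or have the consent form ask separately for use of data.
- Reconcile Section 4 with the control waiver in Section 18, and say whether the 96 counts assigned or consenting patients.

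**Cost.** A waiver for people who were asked and said no is harder to obtain than one for people never approached. There is a little more chart review. Keeping decliners also dilutes the effect. If power is 80% with no refusal and only accepters benefit, it falls with 48 per arm to about 70% at 10% refusal and 46% at 30%, nearly the same under a strong, mild or absent prognosis gap. With 65 per arm, half of the goal of 130 in Section 15, it is about 82% and 58% to 60%. If a doubled discharge rate in accepters is assumed instead, the 48-per-arm figures depend on the model: about 60% and 38% with the strong slow/fast mixture, and 78% and 53% with no mixture.

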### ***Waiver or Alteration of the Consent Process***

For our patients assigned to the control group, a waiver of consent will be requested.

## **19) Process to Document Consent in Writing**

The study should present no more than minimal risk of harm to subjects. Nevertheless, the researchers will be collecting a written informed consent from the study participant, and storing those in a secure filing cabinet until the study analysis is complete (approximately 1 year). The consent document is attached to this submission.

